### 11.2.7. Changes to Planned Analyses

Any changes to the planned statistical analyses made prior to performing the analyses will be documented in an amended Statistical Analysis Plan approved prior to performing the analyses. Changes from the planned statistical methods after performing the analyses will be documented in the clinical study report along with a reason for the deviation.

## 11.3. *General Statistical Methods*

### 11.3.1. Analysis Sets

Effectiveness endpoint analyses will use all available data from all eligible TREATMENT subjects. Eligible TREATMENT subjects for the primary effectiveness endpoint includes all TREATMENT subjects who do not have an implantable continuous ECG recording system (eg. Pacemakers, arrhythmia loop recording systems, ICD, CRT). Eligible TREATMENT subjects for the secondary effectiveness endpoint will include all TREATMENT subjects.

Primary safety endpoint analyses will use data from all available TREATMENT subjects. Safety analysis for ATTEMPT subjects will be limited to the Acute primary safety endpoint events (per definition in section 6.2.1.).

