**POLARx Cardiac Cryoablation system**  
**Post Market Clinical Follow-up study**  
**POLAR ICE**

Study Design	
Prospective, non-randomized, multicenter (international), single arm study.
 
All subjects signing the consent, undergoing the index procedure and treated with the study devices will be followed up for one year.

Planned Number of Subjects	
A minimum of 200 subjects (with the possibility to expand up to maximum 400 subjects) will be included in this study. A minimum of 199 De Novo TREATMENT subjects (i.e. first treatment for AF in the left atrium) for paroxysmal atrial fibrillation (PAF) will be analyzed to establish the continued safety and effectiveness profile of the Cryoablation System and fulfill the PMCF requirements for the submitted labeling of the Cryoablation System. This number represents the minimum number for the primary endpoint statistical hypothesis testing.
 
The entire study cohort will provide information on real-world usage of the Cryoablation System and will be analyzed for secondary objectives. These will include subgroup analysis in selected subjects of interest (including (but not limited to) De Novo ablation versus repeated ablations). These analyses will be non-powered but in case some of these subgroups will be poorly represented in the study, Boston Scientific may propose in the future to extend the sample size to up to 400 subjects.

Planned Number of Sites / Countries	
Approximately 25 centers in Europe and Middle East will be included in the study.

Primary Safety Endpoint	
Safety event free rate at 12 months post-index procedure.
 
Primary safety events will consist of a composite of the following procedure-related and device-related adverse events.
 
Acute primary safety endpoint events, events occurring up to 7 days post-index procedure or hospital discharge, whichever is later, include:
 
 
• Death
 
• Myocardial infarction (MI)
 
• Persistent gastroparesis/injury to vagus nerve
 
• Transient ischemic attack (TIA)
 
• Stroke/Cerebrovascular accident (CVA)
 
• Thromboembolism/Air embolism*
 
• Cardiac tamponade/perforation
 
• Pneumothorax
 
• Serious vascular access complications**
 
• Pulmonary edema/heart failure
 

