### 7.1. ***Scale and Duration***

Approximately 25 sites in Europe and Middle East will be included in the study.

A minimum of 200 subjects (with the possibility to expand up to a maximum of 400 subjects) will be enrolled in the study. A minimum of 199 subjects with De Novo treatment (i.e. first treatment for AF in the left atrium) for paroxysmal atrial fibrillation (PAF) will be analyzed to establish the continued safety and effectiveness profile of the Cryoablation System and fulfill the PMCF requirements for the submitted labeling of the Cryoablation System. This number represents the minimum number for the primary endpoint statistical hypothesis testing.

The entire study cohort will provide information on real-world usage of the Cryoablation System and will be analyzed for secondary objectives. These will include subgroup analysis in selected subjects of interest (including (but not limited to) De Novo ablation versus repeated ablations). These analyses will be non-powered but in case some of these subgroups will be poorly represented in the study, Boston Scientific may propose in the future to extend the sample size to up to 400 subjects.

Each subject will be followed at specific time points after the index procedure: pre-discharge, at 3 months (blanking period), 6 months and 12 months post-index procedure. Therefore, the study duration for each subject is expected to be approximately 12 months.

Subjects will be monitored for recurrences of the arrhythmias by means of clinical visits, ECG and 24-hour Holter monitoring.

Study enrollment is expected to be completed in approximately 12 months. Therefore, the total study duration is estimated to be approximately 24 months.

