### 7.2. ***Treatment Assignment***

Any subject who signs the consent form will be considered enrolled in the study.

Any subject that signs the consent form, has the study device inserted into the body and undergoes the protocol specific treatment for the intended disease (cryoablation) will be assigned to the treatment group.

Enrollment will progress until reaching a minimum of 200 subjects and a maximum of 400 subjects. A minimum of 199 De Novo (ie. first treatment for AF in the left atrium) TREATMENT subjects with PAF is needed for the assessment of the primary endpoint statistical hypothesis testing (section 11.1).

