### 7.3. ***Justification for the Study Design***

Boston Scientific believes that a prospective study on AF treatment with the Cryoablation System device powered for standard safety and effectiveness objective performance criteria is adequate for supporting post market requirements for the assessment of the continued safety and effectiveness of the device after market release in CE mark regions.

According to the most recent guidelines (11) catheter ablation has deemed effective in restoring and maintaining sinus rhythm in subjects with atrial fibrillation. The current study design ensures that the minimal number of subjects with De Novo PAF is reached to ensure testing of the statistical hypothesis and enroll a sufficient number of subjects to allow analysis on real-world usage of the Cryoablation System.

In the context of catheter ablation of AF, adjunctive ablation strategies to PV isolation are currently recommended by clinical guidelines (10) in different conditions including: Cavo-Tricuspid Isthmus ablation, linear ablation lesions in the left atrium or focal ablation of reproducible triggers. These adjunctive strategies can be applied with commercial focal/linear catheters either during a PV isolation procedure or during a repeated procedure, according to site standard of care.

Therefore, the heterogeneous scenarios that an electrophysiologist may encounter when approaching a subject with AF and candidate for catheter ablation could lead to different choices during the procedure.

Accordingly, this study will collect data on instance that may include concomitant or delayed adjunctive ablation strategies with other products and use of different diagnostic products to validate the results such as 3D mapping systems.

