## Attempt

A subject who has given written informed consent, and has any study device inserted into the body but does not receive any Cryoablation application will be classified as "ATTEMPT." Attempts subjects will count towards the enrollment ceiling and will be used for analysis of the endpoints as per section 11.3.1. The original signed Informed Consent must be maintained in the center's subject file. A subject ID will be assigned in the EDC system. These subjects won't be allowed to be re-enrolled in the study.

Attempt subjects will be followed up to 7 days after index procedure or until discharge, whichever is later, for safety purposes. All applicable case report forms in the EDC system will be completed. The original signed Informed Consent and any relevant documentation must be maintained in the center's subject file.

For attempt subjects, at the minimum the following forms must be completed:

- Enrollment and Baseline eCRFs;
- Index Procedure eCRFs;
- Pre-Discharge eCRFs and Day 7 follow-up contact eCRF (if applicable);
- Adverse Event eCRFs or Device Deficiency eCRF for any reportable event (as defined in section 17) that occurs after signing the Informed Consent, up to the point of subject withdrawal;
- Protocol Deviation eCRF, if applicable;
- End of study eCRF.

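### Section 11.3.1 defines both primary analysis sets without the De Novo paroxysmal AF limit that the synopsis and sections 7.1 and 7.2 place on the primary hypothesis tests

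*Combined protocol and SAP*

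**What the plan says.** **Analysis sets (11.3.1).** For effectiveness: "Eligible TREATMENT subjects for the primary effectiveness endpoint includes all TREATMENT subjects who do not have an implantable continuous ECG recording system". For safety: "Primary safety endpoint analyses will use data from all available TREATMENT subjects". An implanted recorder is the only filter on the first set. The second has no filter on TREATMENT subjects.

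**TREATMENT class (9.4, Treatment).** A subject belongs to it after at least one cryoablation application, whatever the AF type or ablation history. The same paragraph puts these subjects into every study analysis.

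**Population for the primary tests.** The synopsis and section 7.1 name at least 199 De Novo PAF subjects and say of that figure: "This number represents the minimum number for the primary endpoint statistical hypothesis testing". Section 7.2 repeats the requirement for De Novo PAF TREATMENT subjects and points to section 11.1. Section 7.3 adds: "The current study design ensures that the minimal number of subjects with De Novo PAF is reached to ensure testing of the statistical hypothesis".

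**Role of the full cohort (7.1).** "The entire study cohort will provide information on real-world usage of the Cryoablation System and will be analyzed for secondary objectives". One subgroup comparison named there is "De Novo ablation versus repeated ablations".

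**Hypotheses and methods (11.1).** The visible text does not restate the population. Section 11.1.1.1 refers to all cohorts, and 11.1.2 and 11.1.2.3 to each cohort. No visible text says what a cohort is.

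**The concern.** Section 11.3.1 is the visible place where analysis sets are defined, and a programmer would build the primary populations from it. It gives one explicit exclusion for effectiveness, so it reads as complete. Followed as written, it sends every treated subject into both tests.

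The eligibility criteria admit AF of any type within guidelines and system indications, and the protocol expects repeat ablations. It also allows expansion to 400 if subgroups are poorly represented, so expansion could add the subjects who do not belong in the confirmatory set.

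At stake is what the two single-arm tests show. Pooling could fail a device that meets a goal in De Novo PAF, or pass one that does not. Choosing the population after results are known would weaken a comparison with a fixed goal.

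**Working it through.** **1. The plan's own figure.** The 199 cannot be confirmed, because expected rates, power and attrition are redacted. Several assumed sets come close. With the normal approximation at one-sided 5% and 10% attrition, safety at 92% against 86% with 80% power needs 178, and 178/0.9 gives 198. Effectiveness at 60% against 50% with 85% power needs 177, and 177/0.9 gives 197. The point does not depend on which set was used.

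**2. Share of other subjects.** With exactly 199 De Novo PAF subjects and everyone treated:
- 200 enrolled: 1/200 = 0.5%
- 300 enrolled: 101/300 = 33.7%
- 400 enrolled: 201/400 = 50.3%

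The last is an upper bound. It needs the optional expansion, and the ceiling of 400 also counts untreated subjects (9.1, 9.4).

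**3. Pass rule.** From 11.1.1.3 and 11.1.2.3, a test passes if the one-sided 95% log-log lower limit exceeds the goal (86% safety, 50% effectiveness). Without censoring, for x failures in n and S = 1 − x/n:

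lower limit = S^exp(1.645 × se), with se = √(x/(n(n − x))) / |ln S|

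| n | 199 | 249 | 300 | 400 |
|---|---|---|---|---|
| Most failures that pass effectiveness | 87 | 111 | 135 | 183 |
| Most events that pass safety | 19 | 25 | 31 | 44 |

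**4. One example.** With 83 failures in 199, S = 0.583, se = 0.0600/0.540 = 0.111, and the limit is 0.583^1.20 = 52.3%, a pass. Add 50 others with 29 failures: 112 in 249 gives S = 0.550, se = 0.0573/0.597 = 0.096, and the limit is 0.550^1.17 = 49.7%, a fail.

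**5. Probabilities.** De Novo PAF failures are Bin(199) and failures in the others Bin(m), with exact binomial sums. All rates are assumptions, and no subject has an implanted recorder.

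| Assumed rates (De Novo PAF / others) | Result | m = 50 | m = 101 | m = 201 |
|---|---|---|---|---|
| Effectiveness 60% / 45% | De Novo PAF pass becomes pooled fail | 16% | 36% | 62% |
| Effectiveness 65% / 50% | Verdicts differ | 1% | 3% | 8% |
| Effectiveness 70% / 50% | Verdicts differ | <1% | <1% | <1% |
| Safety 92% / 86% | De Novo PAF pass becomes pooled fail | 13% | 23% | 32% |
| Safety 86% / 92% | Chance of passing pooled (4% alone) | 11% | 22% | 54% |

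At 60% / 45% the pass probability is 87% in De Novo PAF alone and 72% / 52% / 25% pooled; the reverse switch, fail to pass, is under 1%. With one other subject, disagreement is about 1% or less in each scenario.

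**6. Larger sample alone.** With 60% in both groups, verdicts still differ 8% / 10% / 12% of the time, but 7.2 / 9.8 / 11.9 points of that run from fail to pass. This is a separate effect and not a component of the pass-to-fail figures.

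**The case against.** The passages can be partly harmonised. Section 11.3.1 speaks of endpoint analyses and never of a hypothesis test or performance goal, while the synopsis, 7.1 and 7.2 name the population for the tests. The synopsis (assignment to treatment), 7.3, 9.1 and 11.2.2 point the same way; 11.2.2 mentions the first 199 De Novo PAF subjects who qualify for the primary endpoint analyses. This shows the intent. It does not remove the conflict, because the visible hypotheses and methods restate no population, 11.2.2 only times a report, and 9.4 sends TREATMENT subjects into every analysis.

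Redaction is a fair caution. The sample-size subsections sit inside 11.1, the section that 7.2 cites, and may define the cohorts. That could settle the word cohort, but 11.3.1 would still state a different set.

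The larger figures need assumed rates that nothing visible confirms. The background section cites about 70% and 65% efficacy for another cryoballoon in PAF, possibly with other endpoints. At those rates, with others at 50%, the effect is small. Pooling can also help the device: at 60% / 55% the pass probability goes from 87% to 89% / 89% / 91%. Both points stand.

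A reader might infer three stronger things that the documents do not support:
- That a mixed-population test is planned. The passages above show otherwise.
- That non-paroxysmal AF will certainly enter. This depends on guidelines and system indications that the documents do not spell out.
- That 9.4 makes 11.3.1 the governing rule for TREATMENT subjects. The cross-reference ("will be used for analysis of the endpoints as per section 11.3.1") stands in the Attempt paragraph and concerns ATTEMPT subjects only.

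**Conclusion.** The contradiction is real and should be fixed. The visible rule would run both primary tests on all treated subjects (for effectiveness, those without an implanted recorder), while the rest of the protocol reserves the tests for De Novo PAF. It is a defect in the set definition; the intent is recoverable.

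The size depends on how many others are treated and how far their rates differ. It is negligible near 200 enrolled with 199 De Novo PAF. It stays at about 8% or less at 65% to 70% against 50%, even with 201 others. It is large only when De Novo PAF is close to a goal and many others differ clearly. The direction is not fixed. All probabilities rest on assumed rates without censoring.

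A linked question stays open even on the intended reading. Section 11.2.2 speaks of the first 199 and 9.1 of a total of 199, while the synopsis, 7.1 and 7.2 call 199 a minimum. The plan does not say which subjects enter the one confirmatory test per endpoint.

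**What to change.** - In 11.1 and 11.3.1, state that the confirmatory set for both primary hypotheses is De Novo PAF TREATMENT subjects and, for effectiveness, those who also have no implantable recorder. Report all-TREATMENT results as secondary, as the synopsis and 7.1 already plan for the whole cohort.
- State whether the single confirmatory test per endpoint uses the first 199 qualifying subjects or all of them.
- Align the Treatment paragraph of 9.4 with this.
- Define or delete the word cohort in 11.1.1.1, 11.1.2 and 11.1.2.3, unless the redacted text already defines it.

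The cost is a wording change in 11.1, 11.3.1 and 9.4, with no added data or subjects. Section 11.2.7 already requires that changes made before the analyses be documented in an amended SAP, so this should be done before any primary result is seen.

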##### **Intent**

A subject who has given written informed consent, meets eligibility criteria, but does not have any study devices inserted into the body will be classified as "INTENT". This includes subjects that had been prepared for the procedure (e.g. medication administered) and/or who had non-study devices inserted into the body. Subjects that are enrolled in the study but do not undergo ablation procedure within 90 days from consent signature date must not be reconsented and will be withdrawn from the study and classified as "INTENT". These subjects won't be allowed to be re-enrolled in the study.

There are no follow-up requirements for Intent subjects. Intent subjects will count towards the enrollment ceiling but will not be used for analysis of the endpoints. The original signed Informed Consent must be maintained in the center's subject file. A subject ID will be assigned in the EDC system.

For intent subjects, at the minimum the following forms must be completed:

- Enrollment and Baseline eCRFs;
- Adverse Event eCRFs for any reportable event (as defined in section 17) that occurs after signing the Informed Consent, up to the point of subject withdrawal;
- Protocol Deviation eCRF, if applicable;
- End of Study eCRF.

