#### **10.5.2. Cryoablation protocol**

Preparation activities should be performed as follows:

1. Assessment of presenting rhythm by 12-lead ECG
2. Baseline the fluoroscopy exposure time (Time 0).
3. Place additional diagnostic catheters, for example in the coronary sinus or for pacing the phrenic nerve, at the discretion of the physician.
4. Per institutional protocol, complete transseptal access (single or double).
5. Per the IFU, prepare the Cryo Steerable Sheath. Insert the Cryo Steerable Sheath over the guidewire and advance the sheath across the atrial septum.
6. Per the IFU, prepare the Cryoablation Catheter and the Cryo Mapping Catheter. Insert the Cryo Mapping Catheter into the Cryoablation Catheter. Insert the Cryoablation Catheter into the Cryo Steerable sheath and advance it into the left atrium.
7. Baseline the LA dwell time.

Following the step-wise approach for the ablation procedure is recommended:

8. Navigating and positioning of the balloon
  - a. Advance the Cryo Mapping Catheter and Cryoablation Catheter under fluoroscopic guidance to the proximity of the target PV
  - b. Inflate the balloon while remaining outside of the target PV
  - c. Occlude blood flow by advancing the balloon as necessary but remain outside of the tubular portion of the vein. Confirm and grade the occlusion (per physician's assessment)
  - d. Verify balloon position for complete PV occlusion. Verification may be performed with fluoroscopy and/or contrast injection or other technique (per investigator's discretion).
9. Cryo Ablation of all target PVs
  - a. Perform cryo ablation as per IFU. A minimum ablation time of TTI + 120sec is highly recommended, where possible. If no PV potential is visible, a minimum ablation time of 180sec is highly recommended.
  - b. During each ablation application: annotate the anatomical location of ablation, the time-to-isolation\* (as observed on the PolarMap EGMs and representing the time point when electrical activity disappears) and the ablation duration.

\* Time-to-isolation is required to be captured through the console, when available.
  - c. Wait for the thawing phase to be completed prior to manipulating the Cryoablation Catheter.
  - d. As needed, perform additional cryoablation in the same PV, adjusting the position of the Cryoablation Catheter, if necessary.

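### The plan does not say whether ATTEMPT subjects' acute events enter the safety rate tested against 86%; on the more natural reading they do not, which favours the device

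*Combined protocol and SAP*

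**What the plan says.** Section 11.3.1 (Analysis Sets) has two sentences on safety. The first is "Primary safety endpoint analyses will use data from all available TREATMENT subjects". The second is "Safety analysis for ATTEMPT subjects will be limited to the Acute primary safety endpoint events", with a reference to the event list in 6.2.1.

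Section 9.4 defines the groups. A subject who has any study device inserted "but does not receive any Cryoablation application will be classified as" ATTEMPT; one cryoapplication makes the subject TREATMENT. ATTEMPT subjects are followed to day 7 or discharge, whichever is later, and the same paragraph says they "will be used for analysis of the endpoints as per section 11.3.1". For Consent Ineligible and INTENT subjects, 9.4 rules out use in endpoint analysis.

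Section 7.2 states that a minimum of 199 De Novo "TREATMENT subjects with PAF is needed for the assessment of the primary endpoint statistical hypothesis testing". Section 11.1.1.3 describes the test: a Kaplan-Meier event-free rate at 365 days, with its one-sided 95% log-log lower limit compared with 86%. It names no analysis set. Its only censoring rule is for subjects who withdraw before 12 months.

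**The concern.** Study devices are in the heart before anything is frozen. At step 5 of 10.5.2 the operator is told: "Insert the Cryo Steerable Sheath over the guidewire and advance the sheath across the atrial septum". The study catheters follow at step 6, and the first cryoapplication comes only at step 9. Tamponade or perforation, air embolism, stroke and serious vascular access complications are all listed acute events in 6.2.1, and all can happen at these earlier steps.

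If such an event leads the operator to abandon the procedure, the subject has had no application and is an ATTEMPT. Under a TREATMENT-only test, the event that should count against the device is then what removes the subject from the analysis. The error can only favour the device.

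If the set is left open, it could also be settled after the events are known, and near the decision boundary that choice would decide pass or fail.

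**Working it through.** **Which reading is more natural.**

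- For TREATMENT-only: the first sentence of 11.3.1 names the primary safety endpoint and TREATMENT subjects together. The second opens a separately named analysis. Section 7.2 attaches hypothesis testing to TREATMENT subjects. Section 11.1.1.3 has no censoring rule for subjects whose planned follow-up ends at day 7 or discharge, and a 12-month Kaplan-Meier estimate that included them would need one.
- For inclusion: 9.4 sends ATTEMPT subjects to 11.3.1 for endpoint analysis.

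The first set of passages is stronger, but no sentence settles the point.

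**The plan's own figure.** The 199 cannot be reproduced, because the assumed safety rate and power are not visible in the public text. That is not a fault of the plan. The documented decision rule can be applied instead.

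**Decision boundary.** Inputs: n = 199 (7.2); goal 86% and one-sided 95% log-log limit (11.1.1.3). With e events and no censoring:

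- S = 1 − e/n
- Greenwood term g = √[e / (n(n − e))]
- lower limit = S^exp(1.645 × g / |ln S|)

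For e = 19, n = 199: S = 0.9045, |ln S| = 0.1003, g = 0.0230. The exponent is exp(1.645 × 0.2295) = 1.459, so the limit is 0.9045^1.459 = 0.8638, a pass. For e = 20, n = 199 the limit is 0.8581, a fail. The test passes with at most 19 events.

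**Adding k ATTEMPT subjects with an acute event** to numerator and denominator:

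| TREATMENT events in 199 | Limit without ATTEMPT | k added | Events / n | Limit | Result |
|---|---|---|---|---|---|
| 19 | 86.4% | 1 | 20/200 | 85.9% | reversed |
| 18 | 87.0% | 2 | 20/201 | 85.95% | reversed |
| 17 | 87.5% | 4 | 21/203 | 85.5% | reversed |
| 15 | 88.7% | 5 | 20/204 | 86.15% | still passes |
| 10 | 91.7% | 5 | 15/204 | 89.0% | still passes |

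**Overstatement of the rate.** Let a be the share of device-inserted subjects who are ATTEMPT, p the share of these with a listed event, and r the TREATMENT event rate. The event rate in everyone is (1 − a)r + ap, so leaving ATTEMPT out overstates the event-free rate by a(p − r). The documents give neither a nor p. Assume a = 1–3% and p = 20–50%, and take r = 19/199 = 9.5%:

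- low: 0.01 × (0.20 − 0.095) = 0.001, about 0.1 point
- high: 0.03 × (0.50 − 0.095) = 0.012, about 1.2 points

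**Chance of a false pass.** Suppose the true event-free rate in all device-inserted subjects is exactly 86%, and a proportion q of them are omitted ATTEMPT subjects with an event. The TREATMENT event probability is then (0.14 − q)/(1 − q), and the chance of at most 19 events in 199 is binomial:

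| q (assumed) | TREATMENT event probability | Chance of passing |
|---|---|---|
| 0% | 14.0% | 3.9% |
| 0.5% | 13.6% | 5.5% |
| 1% | 13.1% | 7.8% |
| 2% | 12.2% | 14.5% |

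This ignores event-free ATTEMPT subjects, who would pull the last column down somewhat. The last row lies beyond the range assumed above, where q is at most 3% × 50% = 1.5%.

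**The case against.** The strongest reply is that ATTEMPT subjects are already in. Section 9.4 says they are used for endpoint analysis under 11.3.1 and rules this out for the two groups below them. Section 11.3.1 restricts both effectiveness endpoints to TREATMENT subjects, so safety is the only tested endpoint to which ATTEMPT subjects could contribute. Its second sentence can then be read as limiting which components they contribute, which fits their short follow-up. The 199 in 7.2 is a minimum count, not an exclusion rule. This stands as far as it goes: the inclusive reading is open. It does not state that ATTEMPT events join the tested rate, and it supplies no censoring rule.

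A reader might also infer more than the documents support:

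- **That the plan states an exclusion.** The word only does not appear in 11.3.1; TREATMENT-only is an inference.
- **That any complication before the first freeze drops out.** If at least one application follows, the subject is TREATMENT and the event counts. Only abandoned procedures are affected.
- **That these events are lost.** ATTEMPT subjects are followed through the acute window, their adverse events are recorded, and 11.3.1 gives those events an analysis. The open question is whether they enter the test.

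Finally, one event can reverse any threshold test at its boundary. That is true, and the expected safety rate is not visible, so closeness to the boundary cannot be shown.

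**Conclusion.** The concern holds as an unresolved definition of the primary safety set whose more natural reading biases the tested rate in the device's favour. Its practical size is modest. The result changes only at roughly 17 to 19 TREATMENT events in 199, and with 10 or fewer even five omitted events would not matter. The overstatement of about 0.1 to 1.2 points and the rise in false-pass probability from 3.9% to 7.8% at q = 1% rest on assumed ATTEMPT frequencies, and all calculations assume no censoring. The direction of the bias needs only that ATTEMPT subjects have listed acute events more often than TREATMENT subjects, which is plausible because such an event is itself a reason to stop.

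This should be fixed before analysis. Confidence is moderate, because the TREATMENT-only reading is inferred, not stated.

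**What to change.** In 11.3.1, define the primary safety analysis set as all De Novo PAF subjects with any study device inserted, that is TREATMENT plus ATTEMPT. State that ATTEMPT subjects contribute their acute primary safety events and are otherwise censored at the end of planned follow-up (day 7 or discharge, whichever is later). Repeat the censoring rule in 11.1.1.3. Report the TREATMENT-only rate as supportive. The minimum of 199 TREATMENT subjects can stay, with ATTEMPT subjects counted in addition.

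The cost is wording. Section 9.4 already requires baseline, procedure, pre-discharge, day-7 (where applicable) and adverse-event forms for ATTEMPT subjects, and 11.2.7 provides for an amended SAP approved before analysis. The price to the sponsor is a slightly less favourable safety rate.
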